## 9.3 STRUCTURAL PHARMACOKINETIC MODEL

The population PK model selected on previous data was a two-compartment model with elimination from the central compartment. The model was parameterized in terms of clearance (CL), central volume of distribution ( $V_1$ ), inter-compartment clearance (Q) and peripheral volume of distribution ( $V_2$ ). All parameters were scaled to body weight using fixed allometric rules. The CL was also scaled to eGFR with a power model for pediatric population and a Gompertz function for adult population. Ethnic population covariate was

	PH21036 / GDX-44-015 Analysis Plan Version 2.0: 29/10/2024	gadopiclenol Page 16/30
---	---	----------------------------

applied on all parameters. Exponential models were used to describe the inter-individual variability on CL,  $V_1$  and  $V_2$  and a proportional model was considered as error.

**Figure 1 Structural Gadopiclenol Population PK model**

Further to the submission of gadopiclenol application to health authorities, it was requested by EMA to replace the two equations used to estimate the influence of eGFR on CL of adults and children by a single equation based on serum creatinine (Screat) instead of eGFR. The model used for the application was the one model built on studies GDX-44-003, GDX-44-005 and GDX-44-007 (i.e. without study GDX-44-013 in Japanese volunteers).

Such model was obtained and the relationship between Screat and CL was best described with a 3 parameters Gompertz function as follows:

$$CL_i = \theta \times (1 - A \times \exp(-\exp(-B \times (Screat - C)))) \times \exp(\eta)$$

Where A=asymptote value, B=growth rate and C=inflexion point.

Parameters estimates are presented in Table 2.

	PH21036 / GDX-44-015 Analysis Plan Version 2.0: 29/10/2024	gadopiclenol Page 17/30
---	---	----------------------------

**Table 2 Gadopiclenol population PK model parameters estimates from the model refined for EMA submission and using Serum creatinine as covariate to describe renal function impact on CL**

Parameter	Estimate (%RSE)	95% CI	Variability (CV%) Correlation (R%)
$CL(L/h) = \theta_1(Weight/70)^{0.75} * (1 - \theta_5 * EXP(-EXP(-\theta_6 * (Screat - \theta_7)))) * EXP(\eta_1)$			
$\theta_1$ : CL typical value	5.61 (2.44)	(5.34;5.88)	
$\theta_5$ : Asymptotic (maximal) effect of Screat on CL	0.869 (1.28)	(0.847;0.891)	
$\theta_6$ : growth rate of CL	0.0334 (12.8)	(0.025;0.0418)	
$\theta_7$ : inflexion point of adults CL	110 (3.37)	(103;117)	
$\eta_1$ (IIV CL)	0.0450 (13.3)	(0.0333;0.0567)	CV=21.2%
$Q(L/h) = \theta_2(Weight/70)^{0.75} * EXP(\eta_2)$			
$\theta_2$ : Q typical value	4.15 (8.31)	(3.47;4.83)	
$\eta_2$ (IIV Q)	0.285 (28.0)	(0.128;0.442)	CV=53.2%
$\eta_{2,1}$ (cov CL, Q)	0.043 (39.5)	0.00968; 0.0763	R=38%
$V_1(L) = \theta_3(Weight/70) * EXP(\eta_3)$			
$\theta_3$ : $V_1$ typical value	7.55 (2.94)	(7.11;7.99)	
$\eta_3$ (IIV $V_1$ )	0.0724 (18.2)	(0.0465;0.0983)	CV=26.9%
$\eta_{3,1}$ (cov CL, $V_1$ )	-0.00177 (350)	-0.0139; 0.0104	R=3.1%
$\eta_{3,2}$ (cov Q, $V_1$ )	-0.116 (28.3)	-0.180; -0.0517	R=-80.8%
$V_2(L) = \theta_4(Weight/70) * EXP(\eta_4)$			
$\theta_4$ : $V_2$ typical value	4.80 (4.96)	(4.33;5.27)	
$\eta_4$ (IIV $V_2$ )	0.203 (17.6)	(0.133;0.273)	CV=45.1%
Residual error			
$\epsilon_1$ : proportional component	0.0206 (5.87)	(0.0182 ;0.0230)	CV=14.4%
OFV: 9422.311 - Run number EMA8 Condition Number: 92.2			

This model will be considered as starting point for the modeling including pediatric patients (<2 years old) during structural model refinement. Depending on the preliminary checks, it will be either updated and refined after including pediatric patients <2 years to the existing dataset or considered as initial setting for building a pediatric population <2 years model. The inclusion of Japanese healthy volunteer data from GDX-44-013 study in this model will be performed later when the study on Japanese pediatric patients data will be completed and their data available for updating the model.

Once the structural model will be defined, the residual error model will be refined and finally the IIV will be introduced on the PK parameters for which the estimation of the variability can be supported by the data. At this step the error models will be diagonal (no covariance between variance components will be included).

	PH21036 / GDX-44-015 Analysis Plan Version 2.0: 29/10/2024	gadopiclenol Page 18/30
---	---	----------------------------

The selection of the most parsimonious structural model with appropriate IIV and residual error will be called the BASE model.

#### 9.4 *ERROR MODELS SPECIFICATION (RANDOM EFFECTS)*

Total variability (model errors) will be split as inter-individual and intra-individual components.

In population modelling, each subject is assumed to be sampled from a representative population. Thus, the individual PK profiles can be considered as a random realization of a population PK model, which by extension is equivalent to consider that each individual profile is obtained by a subject specific random realization of each parameter of the model.

The model parameters are thus considered as random effects having a mean value (or typical value) and a variability. These variabilities are the inter-individual variability component.

Other sources of error (noise, error or measurements, model misspecification, etc.) are included in the residual error term and associated with the intra-individual variability component.

The objective of the population PK modelling is to obtain estimates of the typical values and the variability of the parameters, as well as of the residual error.

##### 9.4.1 *Models for inter-individual variabilities (IIV)*

Let  $\theta_i$  refers to the parameter value in the  $i^{\text{th}}$  individual,  $\theta_{TV}$  is the typical value of the parameter in the population, and  $\eta$  is a Gaussian random variable with a mean of 0 and a variance of  $\omega^2$ .

Two models for IIV can be considered:

1. The exponential model:

$$\theta_i = \theta_{TV} e^{\eta_i}$$

The exponential model is useful for a lognormal distribution. In that case  $\theta_{TV}$  denotes the median of the distribution.

2. The additive model:

$$\theta_i = \theta_{TV} + \eta_i$$

The additive model is a standard Gaussian model with constant standard deviation (SD).

As far as possible, the exponential model will be considered for PK parameters in order to ensure strictly positive values. However, in some circumstances, the additive model could provide a better fit and should be considered. The distribution of the random terms will be investigated to determine the best model.

	PH21036 / GDX-44-015 Analysis Plan Version 2.0: 29/10/2024	gadopiclenol Page 19/30
---	---	----------------------------

#### 9.4.2 Model for residual variability

Three different models of residual variability will be tested on measurable plasma concentrations:

The additive error model:  $Y=f+\epsilon$

The multiplicative error model:  $Y=f.(1+\epsilon)$

The mixed error model:  $Y=f+\epsilon_1+f.\epsilon_2$

Where  $Y$  are the observed concentrations,  $f$  are predicted concentration, and  $\epsilon$ ,  $\epsilon_1$  and  $\epsilon_2$  are random variables with a mean of 0 and variance respectively of  $\sigma^2$ ,  $\sigma_1^2$  and  $\sigma_2^2$ .

Residual variability will be expressed as a coefficient of variation (CV) for multiplicative error model and SD for additive model.

Only covariates that were measured or reported in at least 15% of the population will be considered for the covariate model.

As in the previous model, ethnic effect will be included on each parameters in the structural model, the influence of Screat will be included on the clearance in the structural model and the body weight will be included in the structural model using standard allometric scale:

$$CL_i = CL_{pop} \times \left( \frac{Weight_i}{70} \right)^{0.75}$$

$$V_{1i} = V_{1pop} \times \left( \frac{Weight_i}{70} \right)$$

$$Q_i = Q_{pop} \times \left( \frac{Weight_i}{70} \right)^{0.75}$$

$$V_{2i} = V_{2pop} \times \left( \frac{Weight_i}{70} \right)$$

## 9.6 STATISTICAL MODEL SELECTION

Once the BASE model was obtained, influence of predefined covariates will be investigated first using a univariate analysis.

The following procedure will be used for the univariate analysis:

- One covariate effect on a single model parameter is included in the BASE model per run;
- Take care not to include several covariates that are markers of the same feature (e.g. weight and BMI) in order to avoid collinearity. Choose the best;
- Addition of a covariate is significant if the LRT gives a p-value < 0.05 (i.e.  $\Delta OFV \geq 3.84$ );
- Repeat these steps with all covariates and parameters suspected to be affected by the covariates;
- Rank the covariates by size of effect on OFV by comparison to the base model (the largest decrease is ranked 1).

	PH21036 / GDX-44-015 Analysis Plan Version 2.0: 29/10/2024	gadopiclenol Page 21/30
---	---	----------------------------

[figure not shown]
Once the univariate step is complete and covariates were selected, a backward multivariate analysis will be performed:

- Add all significant covariates selected by the univariate steps to the model and get a new OF for this FULL model;
- Proceed to a backward deletion until no covariate can be removed without significantly increasing the objective function:
  - o Remove the covariates once at a time, starting with the weakest obtained by the ranking of the univariate process. Fit to the data, get the OF and compare to the OFV of the FULL model. Decide to keep the covariate in the model if the covariate is significant at the  $\alpha^*$  level where  $\alpha^*$  is an adjusted level insuring a maximal overall 5% type I error over all tests performed.
  - o Repeat this step until all covariates are tested versus the last accepted model.
- When all covariates are tested, get the FINAL model and compute 95% confidence intervals (CI) on the parameters. 95%CI will be computed as  $\theta \pm 1.96 \times \text{SE}(\theta)$ .

Moreover, in order to facilitate the interpretation of the importance or the potential clinical relevance of a covariate instead of relying only on statistical significance, forest plots will be performed with the statistical model including all significant covariates, and it will consist of evaluating the effect of each covariate comparing the 95% confidence interval (CI) of the covariate against a predetermined threshold (5th and 95th percentile, in case of continuous covariates). If the 95% CI is outside the predetermined range, the influence of the covariate can be considered sufficiently large, *i.e.* may be potentially of clinical relevance. If the 95% CI includes 1 (or 100%), the influence of the covariate is statistically non-significant. If the 95% CI is within the range and excludes 1 (or 100%), the influence of the covariate is statistically significant but not sufficiently large to have a potential impact in the clinical context. In other cases, there may be not enough information to conclude about the effect of a covariate, as summarized in [Figure 2](#).

	PH21036 / GDX-44-015 Analysis Plan Version 2.0: 29/10/2024	gadopiclenol Page 22/30
---	--	--

**Figure 2 Tested relevance of covariates in the model**

The range of 0.80 to 1.25, the same as the bioequivalence threshold will be chosen in this analysis. Here it will be called the range of sufficiently large covariate effect because covariate testing will be performed on all parameters showing correlation with studied covariates.

After this step, the final model could be determined.

## 9.7 ESTIMATION METHOD AND MODEL ACCEPTANCE

Due to the rich sampling nature of the data the FOCE method (with  $\eta$ - $\epsilon$  interaction) will be the preferred method *a-priori*.

At each step of the model building, intermediate models will be accepted if:

- Minimization is successful.
- Covariance step finishes without warning message.
- Number of significant digits on parameters is superior or equal to 3.
- Correlation between any 2 parameters ( $\theta$ ,  $\eta$  or  $\epsilon$ ) is inferior to 0.95.
- Absolute values of gradients at last iteration are inferior to 100 but  $> 0.001$  in order to avoid local minima.

For the final model, in addition to these criteria, the following will be evaluated:

- 95%CI of estimates excludes 0. If 0 is included within the 95%CI, this will lead to exclusion of the corresponding parameter from the model unless it will be part of the structural PK model;
- Over-parameterization will be assessed using the condition number for which a value exceeding 1000 is indicative of severe ill-conditioning.

## 9.8 MODELS EVALUATION AND GOODNESS OF FIT

The following diagnostic and goodness of fit plots are applicable at each step of model building:

- Population Weighted Residuals and NPDE versus Population Predicted Concentrations (WRES vs PRED), with a null intercept horizontal line and a trend line;
- Population Weighted Residuals and NPDE versus Time/Time after last dose, with a null intercept horizontal line and a trend line;
- Individual Weighted Residuals versus Individual Predicted Concentrations (IWRES vs. IPRED) , with a null intercept horizontal line and a trend line;
- Individual Weighted Residuals and Absolute Individual Weighted Residuals versus Time/Time after last dose, with a null intercept horizontal line and a trend line;
- Concordance plot of Observed Concentrations versus Population Predicted Concentrations (DV vs PRED), with the line of identity and a trend line, in linear and log scale;
- Concordance plot of Observed Concentrations versus Individual Predicted Concentrations (DV vs IPRED), with the line of identity and a trend line, in linear and log scale;
- Histograms or Q-Q plots of the Population Weighted Residuals (WRES), Individual Weighted Residuals (IWRES) ;
- Histograms or Q-Q plots of the empirical Bayes Estimates (EBEs) of the parameters and/or random effects ( $\eta$ );
- Scatter plot matrix of parameters EBES.

	PH21036 / GDX-44-015 Analysis Plan Version 2.0: 29/10/2024	gadopiclenol Page 24/30
---	---	--

For the covariate models, the following plots will be provided:

- Index plots of EBEs of random effects ( $\eta$ ) against covariates;
- Index plots of residuals (WRES) against covariates.

For the final model, the following plots will be added:

- Individual plots displaying on the same graph (1 figure/panel by subject) the observed, the individual predicted and the population predicted concentrations over time.

Goodness of fit (GOF) plots can be stratified by dose, or any other condition that is deemed relevant (such as health status for example).

Only goodness of fit plots for the BASE and FINAL model will be compiled for inclusion in the popPK dedicated document for results, all other intermediates GOF plots could be generated on request but will not be saved.

For the FINAL model, quality of individual PK parameters estimates will also be assessed using shrinkages.

## 10 EVALUATION OF PREDICTABILITY AND STABILITY OF THE MODEL

Evaluation of predictability and stability of the FINAL model will be performed using prediction-corrected performance visual checks (pcVPC). The pcVPC were shown to be a more powerful diagnostic tool than classical VPC to detect important model misspecifications. Especially because they aims to correct for the differences within a time bin coming from independent variables such as population or time difference within a sampling window.

The pcVPC will be computed and displayed as follow:

- Like for classical VPC, perform a large number of replication ( $N \geq 1000$ ) of the original dataset using the parameters estimated in the FINAL model through Monte Carlo (MC) simulations.
- $pcY_{ij} = Y_{ij} \cdot (PRED_{bin} / PRED_{ij})$

where:

$Y_{ij}$  = observation or simulated prediction for the  $i^{\text{th}}$  individual and  $j^{\text{th}}$  time bin

$pcY_{ij}$  = prediction-corrected observation or simulated prediction

$PRED_{ij}$  = typical population prediction for the  $i^{\text{th}}$  individual and  $j^{\text{th}}$  time bin

$PRED_{bin}$  = median of typical population prediction for the specific bin of independent variable

- The 5%, 50% (median) and 95% percentiles of the original plasma concentration will be calculated and presented graphically over time.
- Simulation-based 90% prediction intervals (defined as the interval between the 5% and the 95% percentile from simulated datasets) will be obtained by time point for the 5%, the median and the 95% percentiles and presented graphically as bands.

A line for the observed median or 5%-95% percentiles moving outside its respective simulation-based prediction interval denote a model misspecification regarding central tendency (median) or variability (5% - 95% percentiles).

## 11 DERIVED VARIABLES

GFR at screening in pediatric population <2 years will be estimated using bedside Schwartz equation:

	PH21036 / GDX-44-015 Analysis Plan Version 2.0: 29/10/2024	gadopiclenol Page 25/30
---	---	----------------------------

$$eGFR (mL/min/1.73m^2) = \frac{0.413 \times \text{height (cm)}}{\text{Serum creatinine (mg/dL)}}$$

By convention, subjects with serum creatinine value BLQ at screening will be imputed a value of eGFR calculated with the LLOQ value of creatinine.

The following PK parameters will be derived from the final population PK model:

Area under the curve:

$$AUC_{0-\infty} = \frac{\text{dose administered}}{CL}$$

Terminal half-life (assuming a 2-compartment model):

$$t_{1/2\beta} = \frac{\ln 2}{\beta}, \text{ where } \beta = \frac{1}{2} [k_{12} + k_{21} + k_{10} - \sqrt{(k_{12} + k_{21} + k_{10})^2 - 4k_{21} \cdot k_{10}}]$$

where:

$k_{12}$  is the rate constant from compartment 1 to compartment 2;

$k_{21}$  is the rate constant from compartment 2 to compartment 1;

$k_{10}$  is the rate constant of elimination from compartment 1.

## 12 SIMULATIONS

The final population PK model will be used to simulate gadopiclenol concentrations at 10 ( $C_{10}$ ), 20 ( $C_{20}$ ) and 30 ( $C_{30}$ ) min after injection as well as AUC, at the doses 0.025 mmol/kg, 0.05 mmol/kg and 0.1 mmol/kg for each population.

The final dataset will be used for the simulations and 1000 replicates of this dataset will be obtained to determine the distribution of  $C_{10}$ ,  $C_{20}$ ,  $C_{30}$  and AUC.

These exposures variables will be compared descriptively by age groups (adults, 12-17, 7-11, 2-6 years and <2 years), by ethnic group and by health status, using descriptive statistics (2.5th percentile, median, 97.5th percentile, geometric mean and CV) as well as graphically using box-plots.

	PH21036 / GDX-44-015 Analysis Plan Version 2.0: 29/10/2024	gadopiclenol Page 26/30
---	---	----------------------------

## 12.1 SIMULATION IN CASE OF TERMINATION OF THE STUDY BEFORE COMPLETION OF THE RECRUITMENT

In the event that recruitment cannot be completed as planned at the end of the study, the exposure and PK parameters in non-recruited age groups will be determined by simulation.

The modeling steps (preliminary checks, model upgrade / refinement and validation) with the data available at end of study will be performed as specified in Section 9 and 10.

The refinement of the model will focus specifically on the impact of SCreat on elimination parameter since it is known that renal function is not mature before 1 year old and the current relationship does not account for the maturation in youngest patients.

In order to simulate a realistic pediatric (<2 years) population of patients in terms of association between gender, age, weight and SCreat levels, the 45 patients from the study DGD-44-063 will be used.

For each age group not recruited and to be simulated, two hundred individuals (100 female and 100 male) will be sampled, with replication, from the DGD-44-063 dataset.

The PK exposure parameters ( $C_{10}$ ,  $C_{20}$ ,  $C_{30}$  and  $AUC_{0-\infty}$ ) for the dose 0.05 mmol/kg will be simulated for these patients from the popPK model obtained after inclusion of the recruited patients.

The same simulations will be performed for all other paediatric age groups and for adults with normal renal function by resampling, for each age group, subjects from the available data (including GDX-44-015 for age group recruited, GDX-44-007 for pediatric subjects above 2 years old, GDX-44-003 and GDX-44-005 for adults with normal renal function).

The distribution of simulated parameters will be summarized graphically using box plots by age group. Moreover, 5th, 25th, 50th (median), 75th and 95th percentiles will be tabulated by age group.

The PK exposure parameters simulated from the refined model will be compared to those simulated from a model where the maturation of renal function is based on post-menstrual age (PMA) instead of SCreat.

The maturation function described by Rhodin *et al.* was used to describe the maturation of the renal fraction of elimination ( $MF_{renal}$ ), as shown in the following equation:

$$MF_{renal} = \frac{PMA^s}{PMA_{50}^s + PMA^s}$$

Where:

- PMA is the post-menstrual age, calculated as the sum of 40 weeks gestational age (assuming a standard gestational age), plus post-natal age;
- $s$  is the sigmoidicity factor ( $s=3.4$ );
- $PMA_{50}$  is the PMA at which  $MF_{renal}$  reaches 0.5 (47.7 weeks).

Therefore, for the simulations of gadopiclenol concentrations in infants, the clearance term in Table 2 will be replaced by:

$$CL = \theta_1 \times \left( \frac{Weight}{70} \right)^{0.75} \times \frac{PMA^{3.4}}{47.7^{3.4} + PMA^{3.4}}$$

The PK exposure parameters ( $C_{10}$ ,  $C_{20}$ ,  $C_{30}$  and  $AUC_{0-\infty}$ ) for the dose 0.05 mmol/kg will be simulated for the same populations and age groups resampled as described above and will be presented in the same manner. Alternative doses could be simulated if necessary.

The simulation workflow is summarized in Table 3.

	PH21036 / GDX-44-015 Analysis Plan Version 2.0: 29/10/2024	gadopiclenol Page 27/30
---	---	----------------------------

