**Table 3 Simulation workflow**

Reference model for simulation	Current model with SCreat level as covariate to account for renal function impact on CL, refined with available pediatric data from study GDX-44-015 available at the time of the analysis.
Population simulated	Age groups not recruited when GDX-44-015 available is terminated
Reference population	Other pediatric age groups (including children above 2 years old) with normal renal function. Adults with normal renal function
Method for simulation of population	Resampling (with replacement) from existing data base
Simulated data	Concentrations at time 10, 20 and 30 minutes after injection Individual CL AUC 0-∞ derived from individual CL
Simulated doses	0.05 mmol/kg
Sensitivity analysis	Same simulations performed with alternate model of maturation of renal function based on PMA (Rhodin et al.)
Method for comparison of simulated data	Graphical display (box-plots) and descriptive tables for distribution of simulated parameters by age group

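### SAP 12.1 prints the PMA clearance equation without EXP(η1), and the SAP 9.2 checks that decide pooling are not required by age group (minor)

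*SAP*

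**What the plan says.** **Simulation for missing groups (SAP 12.1, Tables 2 and 3).** If recruitment stops early, exposure in an age group that was not recruited is simulated. The section states that "the current relationship does not account for the maturation in youngest patients" and that "The refinement of the model will focus specifically on the impact of SCreat on elimination parameter". Exposure is then "simulated for these patients from the popPK model obtained after inclusion of the recruited patients". Table 3 names as reference the "Current model with SCreat level as covariate to account for renal function impact on CL, refined with available pediatric data from study GDX-44-015" and lists as sensitivity analysis "Same simulations performed with alternate model of maturation of renal function based on PMA".

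For the PMA model, "the clearance term in Table 2 will be replaced by" θ1 × (Weight/70)^0.75 × PMA^3.4/(47.7^3.4 + PMA^3.4). No random effect is printed. The Table 2 clearance row ends in EXP(η1), with variance 0.0450 (CV 21.2%) and covariances 0.043 with Q and -0.00177 with V1. PMA-model exposures are simulated "for the same populations and age groups resampled as described above and will be presented in the same manner", that is, as box plots and 5th to 95th percentiles by age group.

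**Pooling decision (SAP 9.1, 9.2, 9.8).** If the existing model predicts the data of patients under 2 years, those data are added to the older data. Otherwise a model is built on patients under 2 years only. Section 9.2 bases this on a prediction-corrected visual predictive check (pcVPC) and on the 9.8 diagnostics, for patients under 2 years as a whole. Section 9.8 allows stratified plots but does not require them. Its plots against covariates are listed for the covariate models, which come after the pooling step.

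**The concern.** **(a) Missing random effect.** If the equation is programmed as printed, two newborns of equal weight and PMA get the same clearance. The spread of simulated AUC then reflects only age and weight, while the creatinine model also carries between-patient variability. The medians would still be comparable, but the percentiles and box plots that 12.1 asks for would not.

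**(b) No age-group panels.** Group 3 may contribute as few as 5 of 45 evaluable patients (11%). The group in which immature renal function matters most therefore has little weight in an overall plot. The check chooses between a pooled model and one of patients under 2 years only. Protocol 11.2, Table 3 gives a relative standard error of 95% for the variability of V1 in the design evaluation, and the text accepts this poor precision for a stand-alone infant model. The team should know which age group drives that choice.

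**Working it through.** **Plan's own figures first.** √0.0450 = 0.212, the CV of 21.2% in Table 2. The maturation factor MF = PMA^3.4/(47.7^3.4 + PMA^3.4) is 0.500 at 47.7 weeks, as 12.1 states. 45/0.90 = 50 patients. All reproduce.

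**(a) Spread of newborn AUC**

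1. AUC = dose/CL (SAP 11). With a dose per kg, AUC is proportional to W/(W^0.75 × MF) = W^0.25/MF, times exp(-η1) if η1 is kept.
2. Without η1: take age uniform over 0-27 days (assumed). The central 90% is day 1.35 to day 25.65, so PMA 40.19 to 43.66 weeks and MF 0.358 to 0.425. Ratio 0.425/0.358 = 1.19. Weight enters only to the power 0.25.
3. Simulated 95th/5th ratio without η1: 1.14-1.21 if weight starts at 3.5 kg and rises 1 kg over 27 days (SD 0.3-0.7 kg); 1.23 if weight is independent of age (mean 3.7 kg, SD 0.5 kg). All weights are assumed.
4. η1 alone: exp(2 × 1.645 × 0.212) = 2.01.
5. Both together, adding log-spreads in quadrature with 1.17 as the middle value: ln 2.01 = 0.698 and ln 1.17 = 0.157; √(0.698² + 0.157²) = 0.715; exp(0.715) = 2.05. Simulation gives 2.03-2.07.
6. Group 2, same method: 1.36 without η1, 2.15 with it.

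C10, C20 and C30 also depend on V1, Q and V2, whose random effects remain in Table 2. The AUC ratios above do not carry over to them.

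**(b) What the overall pcVPC would show**

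The SAP's PMA function serves as a yardstick, not as truth. MF is 0.355 at birth, 0.432 at day 28, 0.589 at 3 months and 0.904 at 12 months. The Table 2 creatinine factor, 1 - 0.869 × exp(-exp(-0.0334 × (Screat - 110))), is 1.000 at 40 and 0.996 at 60 (µmol/L assumed), so it is taken as 1. On this yardstick the existing model overstates clearance 1/0.355 = 2.82-fold at birth, 2.32-fold at day 28, 1.70-fold at 3 months and 1.11-fold at 12 months.

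Smaller misfits tested: 0.432/0.355 = 1.22 and 0.589/0.355 = 1.66 (newborns only), and 0.589/0.432 = 1.36 (Groups 2 and 3).

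Settings: 28, 12 and 5 infants in Groups 1 to 3, Table 2 typical values and variability with covariances, residual variance 0.0206, one sample per window, assumed weights. The main run had 400 trials with 500 replicates each. A trial is flagged if a line leaves its 90% band in at least one of three windows. This is my rule, not the SAP's. Chance alone gives about 1 - 0.9³ = 27%.

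| True misfit in clearance | Overall median | Overall 95% line | Group 3 median |
|---|---|---|---|
| None | 24-27% | 30% | 22-26% |
| 1.22-fold, newborns only | 30% | 41% | 62-63% |
| 1.66-fold, newborns only | 40% | 93-94% | 99% |
| 1.36-fold, Groups 2 and 3 | 90% | not tabulated | 88% |
| Full PMA function (300 trials) | 100% | not tabulated | not tabulated |

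Ranges span repeated runs. The standard error of a 30% rate in 400 trials is √(0.30 × 0.70/400) = 2.3 points, so 30% is hardly separable from 24-27%. In the 1.36-fold case the Group 1 panel is flagged in 25% of trials and Group 2 in 100%, so panels locate a misfit that the overall plot only signals.

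**The case against.** **The missing η1 is probably shorthand.** The allometric equations in SAP 9.5 omit it too, SAP 9.4.1 sets inter-individual variability on parameters in general, and Table 3 lists individual clearance as an output. This stands as the likely intent. But 12.1 replaces an expression that contains the term, so the printed text and the intent should agree.

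**The overall check is not blind.** A reader might infer that Group 1 would hide a maturation misfit. The figures do not support that: with the SAP's own PMA function as truth, the overall median is flagged in every simulated trial. Only a modest newborn-only misfit escapes. A moderate one moves the 95% line, which SAP 10 reads as a matter of variability. Pooling does not lock in a misfit either, because SAP 9.1 brings population specificities into the base model as structural covariates, and age on clearance is tested a priori (SAP 9.5).

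**A reader might infer that exposure in a missing youngest group will be biased because the reference model has no maturation term.** The documents do not support this. Section 12.1 states the limitation, plans a refinement, fully specifies the PMA comparator and presents both models by age group. It is also a contingency: the three groups now enrol in parallel, and Protocol 10.5 continues enrolment to the group minimums.

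**Nor does the single under-2 class in SAP 12 leave the age groups unreported.** Protocol 11.3.6 requires the individual estimates and C10, C20 and C30 by age group.

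**Conclusion.** The point holds as two minor corrections.

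(a) As printed, the PMA equation would give a newborn AUC 95th/5th ratio of about 1.1-1.2 where about 2.0-2.1 is meant, which would invalidate the percentile comparison with the creatinine model. This rests on literal coding, on the Table 2 variance and on assumed age and weight spreads. The η1 contribution of 2.01 needs neither spread.

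(b) The 9.2 checks would reveal a large maturation misfit but are not required to show where it lies, and a newborn-only misfit of about 1.2-fold is barely visible overall. This rests on the PMA yardstick, assumed weights and group sizes, and my flagging rule.

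Neither part shows that the primary analysis is biased.

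**What to change.** 1. In SAP 12.1, print EXP(η1) in the PMA clearance equation and state that the Table 2 covariances with Q and V1 are kept.
2. In SAP 9.2, require the pcVPC and diagnostics for each recruited age group as well as overall, before the pooling decision. Treat a panel of about 5 newborns as descriptive only.

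Cost: SAP wording and a few extra plots; no extra patients, samples or data fields. The downside is a noisy newborn panel, flagged in about 22-26% of trials with no misfit when any one window counts. That is why it should inform the decision and not gate it.

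The PMA term need not enter the main model. PMA is "calculated as the sum of 40 weeks gestational age (assuming a standard gestational age), plus post-natal age", while preterm infants are eligible for Groups 1 and 2, so using it there would be a debatable trade-off.
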